**Mid-intervention testing:**

- Virtual neuropsychological, cognitive, and functional assessments
- Phone call with study staff for patient to report one week's cognitive activity
- Group 2 (mSIM): Participant satisfaction through a survey

**Study equipment break-down (Group 2: mSIM):**

- Delivery company will breakdown and remove equipment from participant's home

**Post-trial testing**, the following will occur:

- Virtual neuropsychological, cognitive, and functional assessments.
- Biomarker draw (blood)
- Physical status assessment including: physical measurements and questions regarding current physical status
- QEEG Assessment
- On-going collection of lifestyle data from FitBit device
- Phone call with study staff for patient to report one week's cognitive activity
- Brain MRI (unless contraindicated based on MRI Safety Screening Questionnaire)
- Group 2 (mSIM): Participant satisfaction with mSIM program through a survey

If participant wants to receive compensation for participation, participant must provide a W9 to study staff before the end of study.

\*The optimal exercise ramp-up duration is 2 weeks based on our prior exercise study in this population. However, participants may require up to 6 weeks depending on their baseline physical activity levels and ability to tolerate the aerobic exercise ramp-up phase. If, after 6 weeks of ramp-up, participants are unable to sustain 40-60%HRR during their exercise sessions, they may then be withdrawn from the trial by the principal investigator.

See **APPENDIX I** for a table view of the study timeline. Note all timepoints might be plus or minus one week.

### Mobile-Based Simultaneous Exercise and Memory Skills Training Program (mSIM):

**Figure 1.** Home set-up of the mobile technology-based simultaneous exercise and memory skills training (mSIM) program.

The mSIM intervention will be carried out in participants assigned to Group 2 (mSIM). Before the in-home training intervention can begin, a research staff member will set-up the participant's equipment while they are on site at PBHC, troubleshoot, plan exercise training days and times, and inform them of the exercise ramp-up procedures. The equipment required for the mSIM home training sessions is compact and low-cost and will include: a folding, stationary exercise bike, Fitbit heart rate and activity monitor synced to the participant's study account, and a tablet to access our mSIM web-based application (see **Figure 1**).

The mSIM participants (Group 2 (mSIM)) will begin by undergoing a minimum of 2 weeks, but up to 6 weeks if necessary, of aerobic exercise ramp-up. Participants will

wear heart rate monitors (FitBit) to self-monitor and ensure that the exercise was completed within their prescribed aerobic target heart rate zone, which is 40-60% heart rate reserve (HRR). The target heart rate zone will be determined by the Karvonen formula, which determines the individual participant's HRR and training zone. The Karvonen Formula is:

$$\begin{aligned} 220 - \text{age} &= \text{maximum heart rate} \\ \text{Maximum heart rate} - \text{resting heart rate} &= \text{heart rate reserve} \\ (\text{Heart rate reserve} \times \text{training\%}) + \text{resting heart rate} \end{aligned}$$

The ramp-up for mSIM participants will start with 2 days per week for 2-6 weeks, where they will be asked to maintain an aerobic intensity of up to 40-60% HRR for 10-40 minutes, depending on their baseline physical activity level. After the ramp-up phase the mSIM (Group 2) participants will begin the 12-week intervention, comprised of 2 times/week, 65-minute sessions. Each mSIM session will include up to 15 minutes of sedentary new memory skills introduction learning or review. They will then have a 5-minute warm-up on the bike (30% HRR), followed by 35 minutes of memory skills training and practice while aerobic cycling in their estimated 40-60% aerobic training zone. They will then have 5 min of interval training which is continuously monitored on the FitBit wrist-worn watch. The resistance level will be pre-set on their bike to meet their aerobic training zone. They will then finish with a 5-minute cool-down that may include a 5-minute summary of skills learned in the session. Participants will be instructed in the importance of staying within their target heart rate zone and not exceeding their heart rate zone. A research staff member will be available during the first 2 weeks of mSIM training sessions via phone to help with any technical issues the participant has during the training session. Participants will be asked to open the FitBit App during their training session to sync their FitBit and indicate the start and stop time of their training session on a session log, so data can be monitored in real-time with the Fitbit data aggregator by research staff and to aggregate study compliance data. All FitBit data will use a de-identified study email address so that no personal identifying data will be linked with either FitBit or the FitBit data aggregator. Participant will be trained on how to ensure they are within their individualized 40-60% HRR and of the safety reasons for not going above 60%HRR.

### **Subject ID Assignment**

Upon enrollment, each participant will be assigned a study ID that will be used to link all data. Only the PI/Sub-PI, and designated members of the research team will have access to a method to link each participant with their subject ID. This database will be password protected and reside within the institution's HIPAA compliant system.

### **Fees for Participation**

There are no costs associated with participating in this research. Routine medical care will be billed to the subject's insurance.

### **Compensation**

Group 1 (activity monitoring group) will receive access to the web-based program after they complete their post-trial testing. All participants will be compensated per completed assessment (\$25.00 x ≤ 3 for neuropsychology testing, \$25.00 x ≤ 2 for QEEG assessment, \$25.00 x ≤ 2 for MRI assessment, \$25.00 x ≤ 2 for blood draw) not done during clinic visits to cover time, travel, and inconvenience. The mSIM participants will be compensated \$10 x ≤ 12 weeks for completing study-related activities, which will be paid out at the end of their study

participation if they have reached at least 80% compliance (19/24 sessions). This includes for the mSIM group: completing mSIM training sessions and homework. The activity monitoring group participants will be compensated the same total amount over the course of the study (\$10 x ≤ 12 weeks) for completing their study-related activities during the intervention, which will be paid out at the end of their study participation if they have reached at least 80% compliance (10/12 weeks). This includes daily wearing of the FitBit for an entire week and weekly syncing of the device, as well as completing cognitive activity monitoring. Parking validation will be provided for study-specific visits. If the participant is enrolled in the RCT and completes all study visits, intervention sessions, data collections, and completed their lab visits and QEEG not during clinic visits, the maximum amount they will receive is \$345. All participants will be able to keep their FitBit after they complete the intervention period.

#### **4. EVALUATIONS AND ASSESSMENTS**

##### Physical Status Assessment

Each participant who is randomized into the RCT will undergo a physical status assessment. During the physical status assessment participants will have their blood pressure, weight, and waist and hip circumferences measured. This assessment will occur at baseline and post-trial for Group 1 and Group 2 participants.

##### Biomarker Data

Each participant who is randomized into the RCT will be assessed for biomarker data. All biomarker data will be collected as fasting AM samples. Participants will have fasted overnight and will not participated in exercise or consumed alcohol or coffee in the past 24 hours.

Fasting blood will be collected for the BDNF and NE analysis at baseline and at post-trial at by nurses or licensed phlebotomists. A nurse or phlebotomist will draw up to 3 tablespoons of blood from the participant's forearm into one whole blood and one serum separator tube. By comparison, the amount of blood collected when people donate blood is 1 pint, or roughly 500 mL. The SJCI lab will conduct sample analysis post-trial via Bionesis and Cat Combi ELISA assay kits using the protocol described in Cat Combi.

##### **Cognitive and Functional Assessments**

Each participant who is randomized into the RCT will be assessed for cognitive and functional abilities using the following assessments:

- NIH Toolbox is administered at screening, mid-intervention, and post-trial.
- The Rey Auditory Verbal Learning Test (RAVLT) is a measure of memory functioning. Administered at screening, mid-intervention, and post-trial.
- Wechsler Memory Scale–Fourth Edition (WMS-IV) Logical Memory I and II is a measure of memory functioning. Administered at screening, mid-intervention, and post-trial.

- Wechsler Memory Scale–Fourth Edition (WMS-IV) Visual Reproduction I and II is a measure of memory functioning. Administered at screening, mid-intervention, and post-trial.
- Oral Trails B is a measure of processing speed. Administered at screening, mid-intervention, and post-trial.
- Functional Activities Questionnaire (FAQ) is a measure of functional impairment. Administered at screening, mid-intervention, and post-trial.
- Multifactorial Memory Questionnaire (MMQ) is a measure of memory functioning. Administered at screening, mid-intervention, and post-trial.
- Montreal Cognitive Assessment (MoCA) is a measure of global memory. Administered at screening, mid-intervention, and post-trial.

### **Medical Record Collection**

A participant's medical record will be collected from their treating physician's office at screening/baseline for medication types, dosage, and frequencies as well as other existing medical conditions and their treatment. The data will be entered into an electronic data capture system by research staff at PBHC. In the event that a particular participant's data has extreme or outlier characteristics, their medical record will be reviewed to identify explanatory factors.

### **Lifestyle Data**

Physical activity, heart rate, and sleep data will be collected automatically and on a nearly continuous basis by using a FitBit activity tracker, or similar commercially-available tracker, which will be provided to each participant in the study.

Participants will be asked to log their cognitive activities for 7 days around the time of their baseline, mid-study, and post-trial time points. We will also collect the IPAQ standardized measure of physical activity at baseline and post-trial time points to obtain a metric of METs of physical activity.

## **5. DATA AND SAMPLE STORAGE AND MONITORING**

### **Data Collection and Storage**

Biological samples may be stored for up to 50 years at a biostorage facility. A code number will be assigned to all samples. Participants' names, medical record numbers, or other identifying information will not be stored with the samples. Participants' names and contact information will be stored at SJC and PBHC and not be shared with researchers outside of SJC and PBHC. Researchers, other than those providing direct medical care, will not have access to personally identifying information.

All biological and questionnaire data described above, but not medical records, will be collected into a centralized secure database and protected by technological, physical, and

administrative safeguards as provided by HIPAA and other applicable privacy laws. Only clinical staff, research staff, and authorized operations personnel will have access to this data. Data may also be de-identified, then stored in a separate secure database for potential future use. SJCI and PBHC will also store archived biological specimens for future research. All samples will be stored as coded samples with no personal identifiers. Codes will be stored separately, password protected, and only accessible to authorized personnel. All cognitive assessment data and medical information collected from subject medical records (e.g., medication and existing medical conditions) will be entered in an electronic data capture system. Research data and de-identified medical information may be stored for up to 50 years at SJCI and PBHC.

### **Data Analysis and Data Monitoring**

The process of analyzing participant study data may continue indefinitely. We will analyze the incoming participant data using multiple regression analysis for statistical changes in clinical health markers over time. Only individuals who have completed all applicable HIPAA training will be provided access to PHI.

### **Data Storage and Confidentiality**

All data will be kept private and shared with the participant as outlined above. Participants' biological data is stored in one database with one set of security credentials and Personally Identifiable Information is stored on a different database with separate security credentials. All data will be stored in a password-protected secured server and only specifically identified study personnel will have access to the data. Discoveries derived from participant data that may be published and shared publicly will have all data de-identified.

## **6. ANALYTICAL METHODS**

To determine feasibility of the protocol, we will analyze adherence and feasibility data from participants via a secure data-aggregation program from which will pull de-identified FitBit session data and also from the session dashboard profiles from the mSIM web-based application. During the intervention, we will collect data related to program adherence in the mSIM web-based application.

In order to determine whether the mSIM treatment protocol produces significant improvements in cognitive abilities, our primary analytic tool will be the linear regression model, which will be implemented as an ANCOVA in SPSS or similarly capable statistical software (e.g., R statistical software and SAS). Outcomes will be the post-trial assessment measurements, baseline measurements of the outcomes will be used as covariates, and treatment group (Group 2 (mSIM) or Group 1 (CON)) will be the key variable to assess the treatment effect.

We will also perform an analysis of peripheral biomarker data to help us understand the biological underpinnings of any cognitive changes produced by the mSIM treatment protocol. Outcomes will be the post-trial biomarker measurements of BDNF or NE corrected concentration levels, baseline measurements of BDNF or NE corrected concentration levels will be used as covariates, and treatment group (Group 2 (mSIM) or Group 1 (CON)) will be the

key variable to assess the treatment effect. We will also conduct an exploratory analysis where we will evaluate the extent to which changes in BDNF and NE separately relate to changes in memory performance (composite memory Z-score) through correlational analyses.

To quantify the effects of the mSIM intervention on cognitive inhibitory tone, we will perform an analysis of the QEEG data. Our primary indicator is a metric called peak Alpha frequency. Outcomes will be the post-trial peak alpha frequency, baseline measurements peak alpha frequency will be used as covariates, and treatment group (Group 2 (mSIM) or Group 1 (CON)) will be the key variable to assess the treatment effect. We will also conduct an exploratory analysis where we will evaluate the extent to which changes in peak alpha frequency separately relate to changes in memory performance (composite memory Z-score) or other biomarker data through correlational analyses. Additional metrics from the QEEG will be explored. EEG will be provided in-kind by Evox and not the NIA-funded study.

An exploratory objective of this study is to test the mSIM treatment response measured with brain MRI. We will analyze functional resting state fMRI, structural MRI, ASL, and DTI data for this study using standard neuroimaging tools to explore structural and functional brain changes related to the intervention.

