### **Data Collection and Assessments**

We will monitor participants in the RCT for up to 26 weeks and perform evaluations to determine cognitive trajectory between the two arms. . Total participation will be approximately 6 months. We will specifically evaluate data consisting of biomarkers (BDNF, NE), QEEG metrics (for example, peak alpha frequency), brain MRI, lifestyle, physical activity, and objective and subjective neurocognition. We will use statistical and computational methods in an effort to explain the causal underpinning of any observed differences between the two arms.

At **pre-screening**, the following will occur:

- Phone screening
- Medical records release to confirm eligibility and determine if they will require additional assessments at screening

At **Screening**, the following will occur:

- Informed consent
- Intake questionnaires
- MRI Safety Screening Questionnaire
- May be required to participate in a brief memory assessment
- PARQ+ and Medical Clearance to Exercise
- Virtual neuropsychological, cognitive, and functional assessments. If clinical neuropsychologist determines that the participant has progressed to dementia or the participant scores below 18 on the MOCA, participant will not pass screening

At **Baseline**, the following will occur:

- Randomization into Group 1 or Group 2
- Biomarker draw (blood)
- Physical status assessment including: physical measurements and questions regarding current physical status
- QEEG Assessment
- Brain MRI (unless contraindicated based on MRI Safety Screening Questionnaire)
- Participant receives Fitbit device and information on usage
- On-going collection of lifestyle data from FitBit device

- Phone call with study staff for patient to report one week's cognitive activity
- Group 2 (mSIM): Participant receives binder with homework to be completed during the course of the mSIM intervention
- Group 2 (mSIM): Participant signs credit card authorization form for damages to study equipment. Form will be shredded at the end of study when participant returns all study equipment
- Group 2 (mSIM): Stationary bike is adjusted for the participant, and they receive instruction on the proper use of the bike
- Group 2 (mSIM): Participant receives instruction on the tablet and mobile application usage

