- Group 2 (mSIM): Participant may be required to see a cardiologist for medical management as part of their standard of care if additional ischemic or hypertensive risk factors are uncovered during the physical status assessment. If participant's blood pressure continues to be above ACSM guidelines and the participant cardiologist will not clear them to participate in a moderately intense, unsupervised exercise program, the participant will be withdrawn from the study 

**Study equipment set-up**, the following will occur:

- On-going collection of lifestyle data from FitBit device
- Group 2 (mSIM): Delivery company will set up study equipment at participant's home
- Group 2 (mSIM): 2 (but up to 6\*) weeks aerobic exercise ramp-up using the exercise equipment provided

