## **10. SUBJECT DISCONTINUATION AND TERMINATION OF STUDY**

Although subjects will be encouraged to complete the study, they may voluntarily withdraw at any time. The investigator will document the reasons for discontinuation.

Also the investigator may withdraw the subject from the study. The subject will be removed from the study without their consent for various health, safety or administrative reasons, including but not limited to the following:

- The investigator decides that continuing in the study would be harmful to subject.
- The sponsor cancels the study.
- Other administrative reasons.

The investigator will make the decision and let the subject know if it is not possible for him/her to participate.

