## **11. COVID-19 PRECAUTIONS**

If needed, depending on the status of the coronavirus pandemic, precautions may be taken to limit the risk of transmitting COVID-19 via study procedures per our institutional policies (Providence Health). Study visits including intake, neuropsychological evaluation at the discretion of the clinician, and physical status assessments may be done using remote procedures. In order to collect physical status assessments, study equipment such as a blood pressure cuff and a calibrated scale may be sent to the participant's home. The participant will be responsible for returning any additional study equipment. Although all COVID-19 related healthy and safety precautions will be addressed throughout this study, some participants may still not be willing to come on-site to PBHC to undergo the mSIM on-boarding session. In this instance then there will be an option for the study staff to perform this in-person visit at their home. Remote visits may continue after the COVID-19 crisis if deemed necessary by the PI or DSMB to preserve the integrity of the research study data. Some study participants may want to further minimize on-site activity. During COVID, participants may request to skip the MRI or QEEG assessments. The following precautions for any in-person study visits may be employed based on the discretion of the PI and institutional policies: screening of participants with questions regarding COVID-19 symptoms/exposure, temperature checks prior to in-person visits, physical distancing as much as possible during the visit, use of personal protective equipment (e.g. masks) during in-person visits, or pre-visit COVID-19 testing.

If a study participant tests positive for COVID-19 and cannot exercise, they may pause participation in the study. They can re-initiate in the study where they left off and the timeline will be paused for up to four weeks and depending on the severity of the case. Participants

Sponsor: National Institute of Health (NIH)

Protocol #: mSIM (NIH 1R21AG061494-01)

Version #/Date: Ver. 04/26-Oct-2021

will be asked to provide medical clearance to re-initiate into the study. The participant may be asked to ramp up exercise for up to 2 weeks at the discretion of the PI and DSMB. If the participant requires more than 4 weeks to re-initiate into the protocol, they will be terminated from the study at that time.

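### Mid-intervention cognitive scores have no role in the treatment-effect analysis, so anyone who leaves after mid-testing drops out of the post-trial ANCOVA: a modest, conditional risk of bias that wording can remove

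*Combined protocol and SAP*

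**What the plan says.** Section 4 (Cognitive and Functional Assessments) lists eight instruments: the NIH Toolbox, RAVLT, WMS-IV Logical Memory, WMS-IV Visual Reproduction, Oral Trails B, FAQ, MMQ and MoCA. Each is "administered at screening, mid-intervention, and post-trial". The mid-intervention visit in section 3 repeats this ("Virtual neuropsychological, cognitive, and functional assessments") with no group restriction, although the satisfaction survey at the same visit is marked for Group 2 only. Both arms are therefore tested three times.

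Section 6 names linear regression, run as an ANCOVA, as the primary tool for cognition: "Outcomes will be the post-trial assessment measurements, baseline measurements of the outcomes will be used as covariates", with treatment group as the key variable. It does not mention the mid scores, a repeated-measures model, an analysis population or the handling of missing scores.

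Two other places hint at longitudinal analysis. Section 3 (Data Collection and Assessments) intends to "perform evaluations to determine cognitive trajectory between the two arms". Section 5 (Data Analysis and Data Monitoring) mentions multiple regression for changes over time in clinical health markers. Neither names the mid scores or a between-arm model that would use them.

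Exits after mid-testing are possible in either arm. Participants are told "they may voluntarily withdraw at any time" (section 10). After a COVID-19 pause of more than 4 weeks, "they will be terminated from the study at that time" (section 11). No dropout rate is given.

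**The concern.** ANCOVA on the post-trial score needs a post-trial score. A participant who completes mid-testing and then leaves contributes nothing, although a full set of scores from part-way through treatment is on file. That score is the best available evidence of how the person was doing shortly before leaving.

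If late leavers in one arm are disproportionately those doing badly, the completers in that arm look better than the arm as randomised, and the ANCOVA reads part of the difference as a treatment effect. Adjusting for the screening score corrects only the part of the selection that the screening score predicts. Differential exit is plausible because mSIM asks for 24 home cycling sessions plus homework, while controls mainly wear a Fitbit. With 15 per arm, each loss is nearly 7% of an arm (1/15).

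**Working it through.** **Inputs from the documents:** up to 30 participants, 15 per arm; tests at three visits; post-trial ANCOVA with the first score as covariate. The plan gives no effect size, SD, correlation, alpha or dropout rate, so it has no figure of its own to reproduce.

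**Assumptions:** scores in SD units; no true effect; two-sided 5% tests; correlations (screening-mid, screening-post, mid-post) of 0.6/0.6/0.7 or 0.7/0.7/0.8; 2, 3 or 5 of 15 leave after mid-testing, in mSIM only. A participant's weight for leaving is proportional to k^(−mid score in SD), so k = 2 means the weight doubles per SD lower. The extreme case is that the lowest mid scorers always leave.

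**Step 1: hand calculation.** If d of 15 leave and their mean mid score is a SD below the arm mean, the completers' mid mean rises by s = a × d/(15 − d). Their post-trial mean rises by r(mid,post) × s and their screening mean by r(scr,mid) × s. ANCOVA removes r(scr,post) times the screening shift, which leaves approximately

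bias = [r(mid,post) − r(scr,mid) × r(scr,post)] × a × d/(15 − d).

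The bracket is 0.7 − 0.36 = 0.34 or 0.8 − 0.49 = 0.31. In the extreme case with d = 3, the lowest 3 of 15 standard normal values have expectations −1.736, −1.248 and −0.948, so a = 3.932/3 = 1.311. Then 0.34 × 1.311 × 3/12 = 0.111 and 0.31 × 1.311 × 3/12 = 0.102 SD. Simulation gives 0.116 and 0.110.

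**Step 2: simulation** (20,000 trials per setting). False benefit shown by the completers' ANCOVA, in SD, for the two correlation sets:

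| Selection on mid score | 2 of 15 leave | 3 of 15 leave | 5 of 15 leave |
|---|---|---|---|
| k = 2 | 0.029 / 0.025 | 0.048 / 0.045 | 0.081 / 0.073 |
| k = 3 | 0.044 / 0.042 | 0.069 / 0.064 | 0.117 / 0.108 |
| k = 5 | 0.059 / 0.055 | 0.086 / 0.079 | 0.142 / 0.130 |
| Lowest always leave | 0.084 / 0.076 | 0.116 / 0.110 | 0.189 / 0.177 |

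A likelihood estimate that uses the mid scores (mid on screening and arm; post on screening, arm and mid) stays within 0.003 SD of zero throughout.

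**Step 3: scale.** The ANCOVA standard error is 0.28 to 0.34 SD. For k = 2 to 5 the bias is 0.09 to 0.43 standard errors and type I error is 5.1 to 7.2%.

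**Step 4: where it vanishes, reverses or cannot be repaired.**
- Same pattern of loss in both arms: bias about 0.
- High scorers leave instead (3 of 15, k = 3): −0.06 to −0.07 SD.
- Random exits of 2, 3 or 5 per arm: no bias; using mid scores cuts the variance by 4–5%, 5–7% or 7–11%, so the standard error by about 2–6%.
- Exits before mid-testing (k = 3): both methods have the same bias, 0.04, 0.06–0.07 and 0.11–0.12 SD for 2, 3 and 5 of 15.

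**Step 5: different assumptions.** With a true effect of 0.5 SD, logistic dropout and a third correlation set (0.7/0.6/0.9), mSIM-only dropout related to a poor mid score gave ANCOVA bias of 0.03 to 0.07 SD at 10% and 0.06 to 0.13 SD at 20%. Using the mid score brought it to within 0.005 SD.

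**The case against.** The strongest reply is that the documented exits do not match the scenario that causes bias. The late-exit rules apply to both arms, and like losses in both arms give no bias. The rules that apply to mSIM alone come earlier. At baseline, if blood pressure stays high and clearance is refused, "the participant will be withdrawn from the study". After a failed ramp-up, "they may then be withdrawn from the trial by the principal investigator". Both act before any mid score exists, so the proposed model cannot recover those people. This stands, and it is why the fix needs a second part.

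Loss after mid-testing may also be small. Post-trial testing is virtual and paid, controls get the web program only after completing it, and a COVID-19 case may pause for up to four weeks and resume. Appendix I, as read, puts mid-testing at month 4 and post-trial testing at month 5, though its columns may have shifted in extraction. These points lower the likely size but do not rule out late exits.

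The gain in power is negligible: with an assumed 0.5 SD effect and random exits of 2 or 3 per arm, it changed by −0.4 to +1.0 percentage points. The case rests on bias, not power. Multiple imputation that includes the mid score would also close the gap with the ANCOVA kept as primary; that is a fair alternative.

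Finally, the hints of longitudinal analysis in sections 3 and 5 mean that use of the mid scores is unspecified rather than excluded. That is correct, but an unspecified use leaves the handling of late leavers to be chosen after the data are seen.

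**Conclusion.** The concern holds. No specified analysis uses the mid-intervention scores, and the ANCOVA as written loses anyone who leaves after mid-testing. Under twofold-to-fivefold selection in mSIM only, with 2 to 5 of 15 leaving, the bias is about 0.03 to 0.14 SD. It reaches about 0.19 SD only if 5 of 15 leave and they are always the lowest scorers.

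These sizes rest on assumed correlations, exit numbers and selection strength, none of which the documents give. The bias requires exits after mid-testing that differ by arm and relate to performance. It is zero with no such exits and about zero if the arms lose participants alike. This is an improvement the plan should make, not a flaw that invalidates it.

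**What to change.** For the cognitive and functional outcomes, specify a mixed model for repeated measures as primary:

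- **Outcomes:** mid and post-trial scores.
- **Fixed effects:** screening score, arm, visit, screening-by-visit and arm-by-visit.
- **Covariance and degrees of freedom:** unstructured 2×2; Kenward-Roger.
- **Primary contrast:** arm difference at post-trial.
- **Population:** all randomised participants with any follow-up score.
- **Sensitivity analysis:** the present ANCOVA.

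State the limits. The post-trial estimate equals the ANCOVA when nobody leaves. The model does not apply to blood, QEEG or MRI outcomes, which have no mid measurement. It does not recover participants withdrawn at baseline or ramp-up.

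For those early exits, report losses by arm and by timing (before or after mid-testing). Add a missing-not-at-random analysis: impute post-trial scores from the available scores, then lower the imputed mSIM scores by 0 to 0.5 SD. At 0.5 SD the arm difference moves by (number lost/15) × 0.5, which is 0.03, 0.07 and 0.10 SD for 1, 2 and 3 lost.

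The cost is wording: no new data or visits, and the model runs in R or SAS, which section 6 already names. The downside is a slightly more complex model in a 30-person trial. Simulated type I error was 4.3 to 4.9% with no exits, random exits or exits after mid-testing. That figure comes from the likelihood estimate with completers − 4 degrees of freedom as a stand-in for Kenward-Roger, not from a fitted mixed model.
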